BISPECTRAL INDEX MONITORING OF
SEDATION IN SPONTANEOUS VENTILATION.
CLINICAL TRIAL IN SCHEDULED
COLONOSCOPIES

January 28, 2018

Bispectral Index Monitoring of Sedation in Spontaneous Ventilation. Clinical Trial in Scheduled Colonoscopies

SUMMARY:

Objective: To compare the monitoring of anesthetic depth in endoscopy rooms using the BIS monitor versus conventional monitoring as a guide for sedation, allowing to offer the best care in terms of patient safety. For this we must ensure that the patient is comfortable, without pain and in the absence of motor response, creating the ideal conditions for the patient and the endoscopist.

Methodology: Randomized double-blind clinical trial in patients undergoing scheduled colonoscopies in endoscopy rooms of the Galdakao-Usánsolo Hospital. We will compare the percentage of optimal sedation (defined as BIS parameter between 65 and 85 or score on the Ramsay scale 2 or 3) as well as the need for rescue medication and incidence of complications among the experimental group in the that sedation is guided by BIS and the control in which the anesthetist is blind to the BIS result.

Expected results: It is expected that the use of the BIS decreases the chances throughout the colonoscopy in which it is necessary to deepen the level of sedation at the request of the patient (presence of pain or dissatisfaction) and / or the endoscopist (patient maintained movement that prevents the realization of the test). No significant differences are expected in total medication dose and major complications.

HYPOTHESES AND OBJECTIVES:

Main hypothesis: The percentage of adequate sedation in the experimental group, guided sedation by BIS, will be 20% higher than in the control group guided by Ramsay.

Secondary hypotheses:

- 1.- The need for rescue medication would increase in the control group.
- 2.-The incidence of hemodynamic, respiratory and other complications would increase in the control group.
- 3.- The total dose of anesthetic medication will be higher in the control group.
- 4.- Satisfaction with the test will be similar in both groups.

Main objective:

Measure and compare the percentage of superficial sedation between the two groups.

Secondary objectives:

- 1.- Measure and compare the doses of rescue medication necessary between the two groups.
- 2.- Measure and compare the incidence of respiratory, hemodynamic and other complications observed during the performance of the test and relate them to the level of sedation.

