- 3.- Measure and compare the dose of hypnotic and analgesic medication used in sedation between the two groups.
- 4.- Compare the level of satisfaction with the test between the two groups.

METHODOLOGY:

- Design: Randomized clinical trial in which the results of two groups of patients are compared.
- Experimental Group (BIS): group of patients in whom sedation is adjusted using as main parameters the information obtained by the BIS sedation monitor (BIS VISTA, Aspect Medical Systems, USA). The BIS target value between 65 and 85, corresponding to a light or moderate sedation, will be considered, noting the parameters obtained at each significant moment of the test.
- Control Group: sedation based on subjective monitoring of the level of sedation, using the Ramsay scale as a reference.

Scope: The endoscopy rooms of the Galdakao-Usánsolo Hospital, which annually performs around 5,000 colonoscopies (4,917 colonoscopies documented in 2016).

Subjects: The reference population is adult patients undergoing a scheduled colonoscopy at the Hospital.

Eligibility criteria:

This target population of the study must meet the following inclusion criteria:

- Patients older than 18 years.
- Scheduled colonoscopy indication.

- Classification of physical status ASA I, II and III, with the exception of patients with lung, kidney and / or liver disease.
- Body Mass Index (BMI) less than 35 kg / m².
- Intact neurological capacity.
- Acceptance to participate in the study after the contribution of written informed consent.

Exclusion criteria:

- Under 18 years old.
- ASA IV.
- BMI greater than 35 kg / m².
- Refusal to participate in the study.
- Allergy to any of the medications used in sedation, or its components.
- Known mental or neurological disease.
- Renal and / or Hepatic Insufficiency.
- Moderate - severe Chronic Obstructive Pulmonary Disease (COPD) or Obstructive Sleep Apnea (SAHS).
- Chronic opiate users.

Sample size calculation: Based on data from a pilot study conducted in our center, we know that the percentage of patients leaving the sedation ranges BIS 65-85 is around 30%. Assuming a percentage of losses of 20% we would need 90 patients per group. It has been calculated with nQuery Advisor v7.0.

ACTING PROTOCOL:

With patients who meet the selected criteria, we will proceed as follows:

- 1) Oral information to the patient of the scientific study to be developed, with completion of the informed consent and delivery of the information sheet.

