- 2) Non-invasive monitoring in the corresponding endoscopy room. Continuous electrocardiography, heart rate, respiratory rate, non-invasive blood pressure, transcutaneous pulse oximetry and capnography will be assessed.
- 3) Positioning of the BIS monitoring system sensor (BIS Quatro™ sensor - BIS VISTA™ monitor - Aspect Medical System) in all patients, regardless of the group to which they are

randomized. To do this, the patient's forehead should be carefully cleaned using a gauze pad soaked in alcohol and left to dry. The sensor is then placed following the manufacturer's instructions.

4) Application of oxygen therapy with nasal glasses maximum 5 L / min connected to a capnography line.

5) Administration of anesthetic drugs following the following protocol: Propofol 1% using the TCI system (Target Controlled Infusion) and Remifentanyl (opioid) intravenously. The rhythms of infusion will be adapted according to the anesthesiologist's judgment to achieve the highest possible degree of comfort, tolerance and analgesia of the patient, depending on the different stimuli provoked during the colonoscopy.

6) All patients will be kept under observation in a space annexed to the endoscopy rooms until their recovery and home discharge, as is usual practice in the Unit. The scale of Aldrete will be used to proceed with the discharge, a score higher than 9 being necessary for this. Patients who do not drive should be advised to perform dangerous or precision activities after 6 to 24 hours after sedation.

These values will be recorded in a paper record during the colonoscopy. This information will be transferred to a database to be carried out in collaboration with the Clinical Research Service of the Galdakao-Usánsolo Hospital.

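### The only rule for when BIS is noted is discretionary and written under the BIS arm; one fixed list of recording points for both arms should replace it

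*Protocol*

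**What the plan says.** - **When BIS is noted.** The Experimental Group bullet (Protocol, Methodology, Design) ends with "noting the parameters obtained at each significant moment of the test". The supplied text has no other timing rule. The Control Group bullet gives none for BIS or Ramsay.
- **BIS as the steered variable.** In the experimental arm "sedation is adjusted using as main parameters the information obtained by the BIS sedation monitor", with 65 to 85 as the target. The Summary describes "the control in which the anesthetist is blind to the BIS result".
- **BIS as an outcome.** The Summary's optimal sedation is "defined as BIS parameter between 65 and 85 or score on the Ramsay scale 2 or 3". The SAP compares superficial sedation using BIS and Ramsay, with no time point and no rule for reducing several readings to one patient result.
- **Who is recorded.** Under Acting Protocol, item 3 places the sensor "in all patients, regardless of the group to which they are" randomized. The closing paragraph adds: "These values will be recorded in a paper record during the colonoscopy". Neither gives an interval, a list of points or a number of readings.
- **When infusions change.** Item 5 lets the anesthesiologist adapt the rates "depending on the different stimuli provoked during the colonoscopy".
- **Planning rate.** The sample size paragraph says that "the percentage of patients leaving the sedation ranges BIS 65-85 is around 30" per cent. It does not say how many readings per patient lie behind that figure.

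**The concern.** An outcome that is also the control signal in one arm needs a measurement schedule that does not depend on what staff see. Here someone must judge which moments are significant. In the BIS arm that judgement can be made with the BIS value in view; in the control arm the anesthetist is blind to it, and the text does not say who notes it.

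A stimulus can prompt both a note and an infusion change, and the text does not say which comes first. A value noted after a correction is more likely to be back in range than one noted before it.

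If the primary result is whether a patient ever left 65–85, as the sample size sentence implies but does not state, its rate rises with the number of readings. Fewer BIS-arm readings, or missed excursions there, would favour BIS. More BIS-arm readings would work against it and cost power.

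**Working it through.** **1. The plan's own figure.** Inputs from the documents: 30% out of range; a 20% difference, taken as 20 points (30% vs 10%); alpha 0.05; 20% losses; 90 per group. Assumed, because not stated: two-sided test, 80% power, continuity correction.

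- Uncorrected: n₀ = [1.96·√(2·0.2·0.8) + 0.8416·√(0.3·0.7 + 0.1·0.9)]² / 0.2² = 61.6.
- Corrected: n = (n₀/4)·[1 + √(1 + 4/(n₀·0.2))]² = 71.25, so 72.
- With losses: 72/0.8 = 90. The stated figure is reproduced.

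**2. A hypothetical model of unequal reading counts.** None of the following is in the documents. A patient fails if any of k noted BIS values is outside 65–85; Ramsay is ignored; 5 readings give the pilot's 30%; within-patient correlation ρ runs from 0 to 0.8.

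- ρ = 0: P(ever left) = 1 − (1 − q)^k, with q = 1 − 0.7^(1/5) = 0.0689. At k = 3 this is 1 − 0.9311³ = 19.3%.
- ρ > 0: beta-binomial with a = q(1−ρ)/ρ and b = (1−q)(1−ρ)/ρ, so P(ever left) = 1 − ∏(b+j)/(a+b+j) for j = 0 to k−1, with q recalibrated to 30% at k = 5. At ρ = 0.5, q = 0.1485; at k = 3 the product is 0.8515 × 0.9258 × 0.9505 = 0.749, so 25.1%. At ρ = 0.8, q = 0.2248 and k = 3 gives 27.8%.

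The chance of p < 0.05 with no true effect was found by exact enumeration at 72 per arm, using the uncorrected chi-square [continuity-corrected in brackets]:

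| BIS-arm vs control readings | ρ = 0 | ρ = 0.5 | ρ = 0.8 |
|---|---|---|---|
| 5 vs 5 | 5.1% [3.3%] | same | same |
| 4 vs 5 | 10.9% [7.6%] | 6.0% [4.0%] | 5.3% [3.4%] |
| 3 vs 5 | 32.8% [25.4%] | 10.3% [7.2%] | 6.1% [4.0%] |

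For 3 vs 5, the part in favour of BIS is 32.7%, 9.9% and 4.8%, against 2.5% with equal counts.

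**3. The opposite direction.** With 8 BIS-arm readings against 5, false significance in favour of BIS falls to between 0.01% and 1.4%. If the truth is 30% vs 10% at 5 readings, power is 56% to 84% [47% to 77%] instead of 87% [82%].

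**4. Missed excursions.** Suppose 10%, 20% or 30% of BIS-arm patients who left the range go unnoted: 30% vs 27%, 24% or 21%. False significance is 7.0%, 13.0% or 24.1% [4.7%, 9.2%, 18.1%].

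**5. The same model applied to the fix.** Three common landmarks instead of five give 19.3% vs 6.1% at ρ = 0 and 27.8% vs 9.1% at ρ = 0.8. Power is then 68% to 85% [59% to 78%] instead of 87% [82%].

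**The case against.** A reader might infer that BIS goes unrecorded in controls, or that the plan prescribes different recording by arm. The documents do not support that. The sensor is on everyone, the paper record is described in the procedure for all patients, and the timing phrase can be read as stages of the colonoscopy, which both arms share. It may sit in the BIS bullet only because the BIS target is introduced there. The form itself, which could list the points, was not supplied, and one part of the SAP was not available.

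A reader might also take 33% as the trial's false-positive rate. It is not. It needs independent readings within a patient and two fewer readings in every BIS-arm patient. At high correlation the excess nearly vanishes, and with the continuity-corrected test several scenarios fall below 5%. The direction is unknown. The model also drops the Ramsay alternative: if Ramsay 2–3 can rescue a BIS excursion, or if the outcome is a share of readings, counts matter less.

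All of this stands, and it limits the claim to an open risk. It does not remove the point. The rule is still discretionary, the arm that steers by BIS still sees it, and unequal timing around an infusion change can matter even when counts are equal or the outcome is a share of readings.

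**Conclusion.** In the supplied text the point holds as an avoidable weakness of design: a discretionary, unlisted recording rule, written under the unblinded arm, for a variable that is both steered and part of the outcome. Differential recording is not shown. The documents give no reading counts, correlation, miss rates or per-patient rule, so the bias cannot be sized or signed. The figures above show only that an ever-left outcome can be sensitive to the schedule, with effects from negligible to large. The change should be made, but this is not evidence that a result would be invalid. Confidence is medium, because the form and part of the SAP were not seen.

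**What to change.** In the Protocol's Design section, replace the event-driven phrase with one pre-printed list of colonoscopy landmarks, the same in both arms. At each landmark, BIS (and Ramsay, if it stays in the endpoint) is written down before any infusion change made there. This governs only the order of recording and changes no dosing rule.

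In the SAP, state that the primary comparison uses these readings, by the same rule in both arms, including how a missed or unreached landmark is handled.

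Match the landmarks to the recording schedule behind the pilot's 30%. If that is not possible, recheck the planning rate and restate the power. A reader might assume that the change leaves 90 per group untouched; step 5 shows that this cannot be taken for granted.

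The cost is a revised form, a few more entries per procedure and a short SAP paragraph. Excursions between landmarks would not count for the primary, but they can be reported separately. Control-arm BIS must in any case be captured by someone or something other than the blinded anesthetist. The documents do not describe staffing, so this should be confirmed.

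### The post-sedation advice in step 6 is garbled: read literally, it addresses only non-drivers, directs them towards hazardous activity and contains no instruction not to drive

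*Protocol*

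**What the plan says.** The relevant text is in the Protocol, section ACTING PROTOCOL.

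- **Step 1** provides for "with completion of the informed consent and delivery of the information sheet".
- **Step 5** specifies the drugs: "Propofol 1% using the TCI system (Target Controlled Infusion) and Remifentanyl (opioid) intravenously".
- **Step 6** opens with a rule for everyone: "All patients will be kept under observation in a space annexed to the endoscopy rooms until their recovery and home discharge". It describes this as the Unit's normal practice.
- **Step 6** then sets the discharge criterion: "The scale of Aldrete will be used to proceed with the discharge, a score higher than 9 being necessary for this".
- **Step 6** ends its discharge instructions with the sentence at issue: "Patients who do not drive should be advised to perform dangerous or precision activities after 6 to 24 hours after sedation".

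The SAP text covers descriptive summaries, group comparisons, the significance level and software. It says nothing about discharge advice.

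**The concern.** The step concerns people who have just received a hypnotic and an opioid and are being sent home. The advice one expects is a temporary ban, for everyone, on driving and on tasks that need full alertness. The sentence differs from that in who is addressed, in what they are told to do, and in the absence of any driving restriction.

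It is a procedural instruction and not background text, so someone following it literally would give wrong safety advice. The stake is the correctness of one patient-safety instruction in a trial whose stated objective includes patient safety. The trial's inference is not at stake.

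**Working it through.** No formula applies and there is no figure in the plan to reproduce. The check has four parts: read the sentence element by element, look for a correction elsewhere, ask whether the defect comes from the way the text was extracted, and look at the interval.

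**1. Literal reading against evident purpose**

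| Element | As written | Evident purpose |
|---|---|---|
| Who is advised | Only patients who do not drive; the relative clause restricts the subject | Every sedated patient |
| What they are advised | To carry out hazardous or precision tasks | Not to carry them out |
| Driving | Appears only in describing who is advised | Prohibited for a time |
| Timing | Once 6 to 24 hours have passed, with the word for *after* used twice | During the 6 to 24 hours following sedation |

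On audience, the same step begins "All patients will be kept under observation in a space annexed to the endoscopy rooms", and step 5 gives the same drugs without distinguishing drivers from non-drivers. Nothing explains why the advice should be limited to non-drivers.

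The only negation in the sentence sits inside the relative clause. If it is moved to follow the verb of advising, and the relative clause is dissolved, the sentence becomes ordinary post-sedation advice. This supports a displaced negation as the cause. The repeated *after* is a further sign of garbling.

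**2. Is it corrected elsewhere?**

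Word counts over the protocol and SAP text examined:

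- *drive*: 1 (this sentence)
- *driving*: 0
- *dangerous*: 1 (this sentence)
- *precision*: 1 (this sentence)

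There is therefore no second statement that could override this one. Two neighbouring provisions might seem to help, but they do not:

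- The Aldrete threshold decides when a patient may leave, not what the patient may do afterwards.
- The reference to usual Unit practice is attached to observation until recovery and discharge, not to the advice.

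**3. Is it an artefact?**

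The sentence is complete and unbroken, with no redaction, gap, table or figure nearby. It is current text, not a description of superseded wording.

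**4. The interval**

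Even with the negation restored, 6 to 24 hours is a range and not a minimum. Its ends differ by 24 − 6 = 18 hours, and the text does not say which applies to whom.

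**The case against.** The best counter-argument is that this is a translation slip with little practical consequence. The English shows other marks of translation, for example in the terms for the nasal oxygen device and the infusion rates. The trial runs at one hospital, and staff may have worked from a correct original. Anesthesiologists and endoscopy nurses would see what was meant. The garbled sentence still conveys a delay, so it does not endorse hazardous activity immediately after discharge. The advice does not differ by arm and touches no endpoint. The information sheet in step 1 is the natural place for such advice and may well be right.

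Much of this stands, and it limits the finding in three ways:

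- It supports the lowest severity.
- It means that the absence of a driving restriction can be asserted only for this sentence and the text examined, not for what patients were told.
- It shows that restoring the negation is not enough, because the interval should also be settled.

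The objection does not rescue the sentence. A reader who can guess the intent is correcting the protocol, not following it. Whether a correct original exists cannot be determined from the documents. If the information sheet is correct, the protocol as written conflicts with it.

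**Conclusion.** The concern holds: the sentence is wrong as written. Its size is one sentence, rated minor, with high confidence. It has no effect on design, sample size, endpoints or analysis, and no harm to participants is claimed.

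That the sentence is defective rests on its wording alone. Two further points are inferences or limits:

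- The displaced negation is the probable cause, not an established one.
- The patient information sheet and consent form were not examined, nor was a part of the SAP file. Any of these, or the Unit's usual practice, may already give the advice correctly.

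**What to change.** Replace the sentence in step 6 with wording such as:

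> *All patients should be advised not to drive, and not to undertake dangerous or precision tasks, for 6 to 24 hours following sedation.*

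This keeps the protocol's own interval and brings in no outside figure. The responsible clinicians should confirm the interval against the Unit's usual discharge advice, and preferably state one minimum period in place of the range. They should also check that the information sheet says the same.

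The cost is one corrected sentence and one document check. Design, data collection and analysis are unchanged.

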## **STATISTICAL ANALYSIS PLAN**

A descriptive analysis of the sample will be carried out by means of frequencies and percentages for the categorical variables and by means and standard deviation or median and interquartile range for the continuous variables.

A comparison will be made between the experimental and control groups of the study with respect to superficial sedation (measured by the BIS and Ramsay), as well as the need for rescue medication and incidence of complications. For this, in the case of continuous variables, the Student's test or the nonparametric Wilcoxon test (when normality is not met), and the chi-square or the Fisher exact test (when the expected frequencies are lower than 5) for categorical variables.

Statistical significance will be assumed when  $p < 0.05$ . All statistical analyzes will be carried out using SAS 9.4 software. Copyright, SAS Institute Inc. SAS and all other SAS Institute Inc. product or service names are registered trademarks or trademarks of SAS Institute Inc., Cary, NC, USA.
